#### 4 STUDY DESIGN

This is a randomized, open-label, single site study conducted in 100 vaccinated healthy adults age  $\geq$  18 to  $\leq$  60 years old in the US.

Subjects meeting inclusion/exclusion criteria will be randomly assigned to one of the four groups through a computer generated process.

Rabies vaccine will be administered to subjects who have been randomized into four groups. Group 1 will receive Chloroquine (po) for 14 days prior to first rabies vaccination. Group 2 will receive Malarone (po) for 14 days prior to first rabies vaccination. Group 3 will receive Doxycycline (po) for 14 days prior to first rabies vaccination. Group 4 (control) will begin rabies vaccination without antimalarial prophylaxis. See Table 1 for group allocation and number of subjects per group

Table 1. Schedule of vaccine administration and subjects per group

Day	0	3	7	14	17	21	28	Number of subjects
Group 1 Chloroquine				IM	IM	IM	IM	25
Group 2				IM	IM	IM	IM	25
Malarone								
Group 3				IM	IM	IM	IM	25
Doxycycline								
Group 4 Controls	IM	IM	IM	IM				25

Blood samples will be taken at most visits for RFFIT assays. Samples will also be taken or exploratory proteomic and cellular assays.

In all groups additional blood samples may be taken if required to assess AEs. Additional biological samples (e.g., body fluid, tissue samples) may be collected in the event of an AE, or SAE.

Clinical site personnel will record immediate unsolicited AEs that occur within 30 minutes after receiving the rabies vaccine. The occurrence of SAEs will be collected throughout the study.

Expected study duration for Groups 1-3 once enrolled in the study is approximately 2 months. Expected study duration for Groups 4 once enrolled in the study is approximately 1 month.

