#### 5 STUDY ENROLLMENT AND WITHDRAWAL

Healthy subjects will be recruited from Syracuse and the surrounding area for participation in this clinical trial.

Enrollment will continue until 25 subjects are vaccinated in each group. Any subject withdrawing prior to first vaccination will be replaced. Any subject withdrawing after first vaccination will not be replaced.

Subjects will be compensated at each study visit. Specifics of compensation is included in the informed consent and approved by the Upstate IRB.

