#### Day 14 (+/- 1 day) Vaccination #1

- Review contraindications to confirm eligibility.
- Perform urine pregnancy test
- Review medical history and note any changes.
- Conduct targeted physical exam, including collection of vital signs and temperature
- Review concomitant medications.
- Record any adverse reaction(s).
- Collect blood for Research Assays (must be completed prior to vaccination)
- Confirm group assignment
- Group 1: Collect urine specimen
- Group 1: Administer chloroquine 500 mg po OR
   Groups 2 and 3: Review drug accountability
- Inject RabAvert® vaccine 1.0 mL IM in deltoid.
- Observe subject for 30 minutes and record any adverse reaction(s).

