#### 7.6 Group 4 (Controls)

#### Day 0 Vaccination #1

- Collect blood for Research Assays (must be completed prior to vaccination)
- Confirm group assignment
- Inject RabAvert® vaccine 1.0 mL IM in deltoid.
- Observe subject for 30 minutes and record any adverse reaction(s).

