## 9.2 Time Period and Frequency for Event Assessment and Follow-Up

Unanticipated problems will be recorded in the data collection system throughout the study.

The PI will record all reportable events with start dates occurring any time after informed consent until study completion. At each study visit, the investigator will inquire about the occurrence of AE/SAEs since the last visit. Events will be followed for outcome information until resolution or stabilization.

Any SAE that occurs after a subject has completed the study but that is likely to be related to the product or to the experiment must also be reported as soon as possible.

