Secondary Objective: To evaluate GMT over protective titer prior to third dose, fourth dose and 28 days post fourth dose of PCECV.

Immunogenicity will be assessed descriptively using the following parameters:

Timepoints: prior to third and fourth dose of rabies vaccine and 28 days after fourth dose of vaccine

A table that presents, by group, the total number of per protocol subjects and the GMT against rabies prior to the third and fourth dose of vaccine and 28 days after fourth dose of vaccine will be produced.

Statistical Methods for Adverse Events and Serious Adverse Events

For each treatment group, a line listing by subject that describes adverse events and post-baseline day of occurrence of the AE will be produced.

The number and percent of subjects in each group who reported any AE between Days 0 and 372 will be summarized in tabular format.

A table showing the number and percentage of subjects in each group who reported adverse events by general type (category) of event will be produced.

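### The SAP's adverse-event window to Day 372 fits no follow-up in this trial, and the adverse-event percentages cover a nominal 56 days in the drug groups against 42 in control, with no split by period

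*SAP*

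**What the plan says.** The SAP's section on adverse and serious adverse events plans three outputs.

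- A by-subject line listing for each group, carrying the "post-baseline day of occurrence of the AE".
- An overall table: "The number and percent of subjects in each group who reported any AE between Days 0 and 372 will be summarized in tabular format".
- Likewise a category table, for subjects who "reported adverse events by general type (category) of event", with no time window stated.

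The section names no denominator for these percentages and plans no table by study period.

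The protocol sets the timing. In Section 7.5, Groups 1–3 take their first antimalarial dose on Day 0, are first vaccinated at "Day 14 (+/- 1 day) Vaccination #1", and have their last visit at Day 56 (±7). In Section 7.6, control starts at "Day 0 Vaccination #1" and has its last visit at Day 42 (±7). Section 4 puts participation at about two months for Groups 1–3 and says of control: "Expected study duration for Groups 4 once enrolled in the study is approximately 1 month". Section 9.2 governs collection: "The PI will record all reportable events with start dates occurring any time after informed consent until study completion". Section 5 adds: "Any subject withdrawing prior to first vaccination will be replaced".

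**The concern.** There are two linked problems.

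The first is a wrong figure. Day 372 belongs to no visit, window or duration in this trial. It may have been carried over from another plan: the SAP's baseline section also speaks of six groups in a four-group trial. The documents do not confirm the origin.

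The second comes from the schedule and would remain if 372 were simply corrected to the last visit. Because the clock starts at Day 0 in every group, the overall and category tables pool a 14-day antimalarial-only lead-in with the vaccination period in Groups 1–3. Control has no matching period. A higher percentage in a drug group could then reflect a drug reaction during the lead-in, an effect during the vaccination period, or only longer observation and more enquiries. The tables would not show which.

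The unstated denominator adds to this. Controls are vaccinated on Day 0, whereas Groups 1–3 spend two weeks on drug first, and anyone who leaves in that time is replaced. A denominator of vaccinated subjects would drop people who left because of a lead-in reaction.

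**Working it through.** **Can Day 372 be reproduced?** The candidates are the last nominal visits (56 and 42), the latest permitted visits (56 + 7 = 63 and 42 + 7 = 49), and the longest spans from the earliest screening day (60 + 63 = 123 and 60 + 49 = 109). None gives 372. It lies 372 − 63 = 309 days beyond the latest visit in Groups 1–3 and 372 − 49 = 323 days beyond it in control. Section 9.2 allows later reporting only of serious events likely to be related, and sets no end day for it.

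**Follow-up and enquiries** (protocol Sections 7.5 and 7.6; AE/SAE rows of Appendices A and B):

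| | Groups 1–3 | Group 4 |
|---|---|---|
| AE visits (days) | 0, 7, 14, 17, 21, 28, 31, 35, 42, 56 | 0, 3, 7, 14, 17, 28, 42 |
| Number of AE visits | 10 | 7 |
| Number from dose 1 onward | 8 | 7 |
| Day 0 to last visit, nominal | 56 days | 42 days |
| Same, within visit windows | 49–63 days | 35–49 days |
| Dose 1 to last visit, nominal | 56 − 14 = 42 days | 42 − 0 = 42 days |
| Same, within visit windows | 49 − 15 = 34 to 63 − 13 = 50 days | 35–49 days |

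Counted from Day 0, nominal follow-up differs by 14 days (56/42 = 1.33). Counted from dose 1, it is equal. The whole nominal difference is the lead-in.

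**Size of the effect on percentages.** The documents give no AE rate, so the following is an illustration with no drug effect. Let p be the assumed control risk by Day 42, and H = −ln(1 − p) the cumulative hazard. Let f be the share of H that is constant background; the rest follows vaccine doses and so is the same in all groups. The 14 extra days add background hazard only:

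risk over 56 days = 1 − exp[−H(1 + f × 14/42)]

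With p = 0.30 and f = 1, H = 0.357 and the risk is 1 − exp(−0.357 × 1.333) = 37.8%, an excess of 7.8 points.

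| Background share f | Excess, p = 20% | Excess, p = 30% | Excess, p = 50% |
|---|---|---|---|
| 1 | 5.7 points | 7.8 points | 10.3 points |
| 0.5 | 2.9 | 4.0 | 5.5 |
| 0.25 | 1.5 | 2.0 | 2.8 |
| 0 | 0 | 0 | 0 |

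At p = 30% the excess is 1.96, 1.01, 0.51 or 0 subjects in a group of 25. The illustration ignores the three extra enquiries and any real drug reaction in the lead-in.

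**The case against.** The strongest case is that little turns on this. Day 372 truncates nothing, and both the SAP's general methods and protocol Section 12.2.1 make clear that events from the whole trial are to be summarised, so the number could be corrected editorially. The unequal follow-up is a separate matter. There is no safety objective and no formal testing is planned. The lead-in is part of the assigned regimen, so an on-study count by regimen is a legitimate description. The listing gives the event day and start dates are recorded, so lead-in events could be picked out later. With 25 per group and a 30% risk, the standard error of a difference is √(2 × 0.3 × 0.7/25), about 13 points, so little could be read from these percentages even with equal follow-up.

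Much of this stands as a limit on importance. It does not remove the problem. The SAP itself specifies percentages by group, which readers will set side by side. Imprecision does not excuse an avoidable difference in observation time, and a listing is not a summary.

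Three smaller points also stand. Events between consent and Day 0 are collected but fall outside the SAP window, so the table is not quite an on-study count. A separate lead-in table cannot divide drug reaction from background, because control has no lead-in. And antimalarials continue through the vaccination period, so that period still mixes drug and vaccine.

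**Conclusion.** The concern holds. Day 372 is an error that in itself changes no count. Followed as written, the overall and category tables would compare a nominal 56 days and 10 enquiries in Groups 1–3 with 42 days and 7 enquiries in control, and would merge a drug-only period with the vaccination period. With no drug effect, the illustrative distortion runs from 0 to 10.3 points over control risks of 20% to 50%. Its true size is unknown: it depends on an AE rate and a background share that the documents do not give. The schedule facts are certain. The change should be made, but its reach is limited: safety is descriptive, and the comparison of geometric mean titers is untouched.

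**What to change.** Replace the Day 0 to 372 window with two defined periods, applied to both the overall and the category table, and assign each event by its start date.

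1. **Vaccination period, all four groups:** dose 1 to the visit 28 days after dose 4 (nominally Days 14–56 in Groups 1–3 and Days 0–42 in Group 4). The denominator is subjects who received dose 1.
2. **Antimalarial lead-in, Groups 1–3 only:** Day 0 to just before dose 1. The denominator is everyone who took at least one antimalarial dose, including those who withdrew before vaccination and were replaced.

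An overall on-study count can be kept if it is labelled as covering unequal follow-up. Show actual days of follow-up by group beside each table. In the listing, give the event day relative to dose 1 as well as Day 0, and include any events between consent and Day 0.

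The cost is SAP wording and one extra set of tables. No new data are needed, because start dates are already recorded. Some inequality remains: from dose 1, Groups 1–3 still have 8 enquiries against 7, and the visit windows allow 34–50 days against 35–49. Those ranges assume no postponed vaccination, which protocol Section 5.5.1.1 permits.
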